### **5.3 INCLUSION OF WOMEN AND MINORITIES**

Both men and women and members of all races and ethnic groups are eligible for this study.

### **5.4 SUBJECT WITHDRAWAL**

Any time prior to the planned surgical procedure, the patient may withdraw from this observational study for any reason without prejudice.

## **6 STUDY PROCEDURES**

### **6.1 BASELINE EVALUATIONS**

Standard presurgical assessment with labs and studies as determined by the preoperative Anesthesia clinic based upon their established guidelines.

The following will be performed within 1 week prior to the planned microscopic observation:

- Informed consent: Must be completed prior to receiving any study-related procedures.
- Medical history
- Physical examination, including vital signs (i.e., temperature, heart rate, respiratory rate, blood pressure, body weight, and height).
- If determined to be eligible for the study and after giving informed consent, a skin-prick test to determine sensitivity and risk of anaphylaxis to fluorescein and a patch test for ICG will be

performed by the Principal Investigator. For testing allergic response to fluorescein, a sterile Duotip® lancet (Lincoln Medical, USA) is used in 3 separate areas of skin on the forearm. The skin-pricks will include 4 microliters of 10% fluorescein, histamine chloride (10 mg/ml) [positive control], and 50% saline solution [negative control] administered in areas of skin prepped with an alcohol pad. After 30 minutes, the appearance of a wheal greater than 3 mm in diameter is considered a positive test result in the context of the appropriate positive and negative control. If a positive test is noted, the patient will no longer be eligible for this study. For comfort and relief of any skin irritation/pruritis, the patient will be offered an anti-histamine (fexofenadine [Allegra®] 30 mg po x 1) following the skin-prick test if necessary. The patient will also be screened for a history of allergic reaction to iodine or iodinated contrast dyes.

- If indicated by anesthesia pre-op assessment (standard operating procedure for pre-op clinic)  
- Hematology [i.e., CBC (with or without differential, auto or manual), ANC, and platelets].
- A complete metabolic panel (CMP): chloride, Co2, potassium, sodium, BUN, glucose, calcium, creatinine, total protein, albumin, total bilirubin, alkaline phosphatase, AST, ALT, A/G ratio, BUN/creatinine ratio, osmol (Calc), anion gap).
- If indicated by anesthesia pre-op assessment (standard operating procedure for the pre-op clinic) – 12-lead electrocardiogram, chest x-ray, and/or pulmonary function tests if indicated. These tests are not strictly required to support eligibility for this study, but if indicated and performed, may exclude the patient from receiving a general anesthetic and therefore, a wide excision performed in the operating room (thereby excluding the patient from this study).
- Pregnancy test (urine) in females of childbearing potential. Females who have undergone surgical sterilization or who have been postmenopausal for at least 2 years are not considered to be of childbearing potential. The standard operating procedure for all females of childbearing potential is to obtain a urine HCG (or a serum HCG if urine unable to be obtained). If the pregnancy test is positive, the patient is excluded from the study.

## 6.2 EVALUATIONS PERFORMED AT END OF TREATMENT

- Standard Post Anesthesia Care Unit (PACU) protocols for patient recovery from surgery. Patients will be continuously monitored for any reaction to either dye both intraoperatively and during the recovery period. Adverse events will be recorded throughout the time of entry into the operating room until the post-operative follow up. If the patient is transported directly to the Intensive Care Unit (ICU), these protocols will also be performed.

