### 6.3 POST-TREATMENT FOLLOW-UP EVALUATIONS

- Standard follow-up and safety evaluations from surgery includes a post-op visit at 2-3 weeks and scheduled follow-up based upon final staging of the patient's cancer. Follow-up will be based upon current NCCN guidelines.

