## 7.2 SERIOUS ADVERSE EVENTS

### 7.2.1 DEFINITION

A serious adverse event (SAE) is any adverse event (experience) that in the opinion of either the investigator or sponsor results in **ANY** of the following:

- Death.
- A life-threatening adverse event (experience). Any AE that places a subject or subject, in the view of the Investigator or sponsor, at immediate risk of death from the reaction as it occurred. It does **NOT** include an AE that, had it occurred in a more severe form, might have caused death.
- Inpatient hospitalization or prolongation of existing hospitalization (for > 24 hours).
- A persistent or significant incapacity or substantial disruption of the ability to conduct normal life functions.
- A congenital anomaly or birth defect.
- Important Medical Event (IME) that, based upon medical judgment, may jeopardize the subject or subject and may require medical or surgical intervention to prevent one of the outcomes listed above.

Elective hospital admission (including planned treatment for progressive disease or a planned protocol procedure), admission for socioeconomic reasons, and death due to tumor progression will not be considered an SAE.

All SAEs will be collected from the date of subject or subject signing consent until 30 days after the last dose of study drug and/or procedure.

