## 11 STUDY RESPONSIBILITIES

### 11.1 DATA COLLECTION

Data entry into the database is to be completed in a timely fashion (approximately within 28 days) after the subject's clinic visit. If an AE is considered serious it is captured on both the Adverse Event page and the Serious Adverse Event Form, which is handled in an expedited fashion.

Data management activities will be performed using EXPeRT. EXPeRT is a suite of software tools that enables the collection, cleaning and viewing of clinical trial data. CRS data management will design the study-specific database and facilitate its development by the EXPeRT Information Technology team. Once the database design is approved by the Investigator, Statistician, and Clinical Research Coordinator, the database will be put into production and data entry can begin. Data can be entered and changed only by those with the rights to do so into the eCRFs. EXPeRT is compliant with all relevant technical aspects of relevant GCP guidelines.

- The system can generate accurate copies of stored data and audit trail information in human readable form.
- System access is limited to authorized individuals through the controlled assignment of unique ID and password combinations.
- The system is designed to periodically force users to change their passwords and verifies that user ID and password combinations remain unique.
- The system automatically generates a permanent time-stamped audit trail of all user interactions.

When data entry is complete, data management will review the data and will query any missing, incomplete, or invalid data points for resolution by the Clinical Research Coordinator and Investigator. Once all queries have been resolved, the data can be released to the statistician for analysis.

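### Adverse-event recording opens at operating-room entry, so non-serious reactions to the study's own preoperative dye tests fall outside the only stated recording period

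*Combined protocol and SAP*

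**What the plan says.** Section 6.2 sets the period for adverse events (AEs): "Adverse events will be recorded throughout the time of entry into the operating room until the post-operative follow up". It gives no day for the end. Section 6.3 says that standard follow-up "includes a post-op visit at 2-3 weeks and scheduled follow-up based upon final staging of the patient's cancer". The Study Calendar has a single post-operative column.

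Section 7.2.1 sets a different period for serious adverse events (SAEs), running from the subject "signing consent until 30 days after the last dose of study drug and/or procedure".

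Section 6.1 places two study tests before surgery, once the patient is found eligible and has consented: "a skin-prick test to determine sensitivity and risk of anaphylaxis to fluorescein and a patch test for ICG will be" performed by the investigator. An antihistamine is offered if the skin becomes irritated. Section 1.2 confirms that patients who are ineligible or do not consent are not skin-tested.

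Section 7.1.3 asks for all AEs to be documented, with Table 1 marking every grade and attribution, but ties this to a collection period that section 7 does not define for AEs. Section 11.1 adds: "If an AE is considered serious it is captured on both the Adverse Event page and the Serious Adverse Event Form". Section 9 describes AE and complication rates by upper one-sided 95% Clopper-Pearson limits and states neither a time window nor a denominator.

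**The concern.** A participant first meets study dye at the preoperative tests, not in the operating room. If section 6.2 is followed as written, a non-serious reaction to the prick or patch is not recorded as an AE. Yet it would meet the broad AE definition in section 7.1.1, and Table 1 would have it reported even at Grade 1. It also bears on safety: section 1.2.2 says that allergic sensitization to fluorescein can increase with each use, and those who pass the tests go on to receive the dye intravenously. The ICG patch test has no reading criterion in section 6.1 and no line in the Study Calendar, so AE recording is the natural place for a reaction to it.

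The second issue is consistency. Serious events come onto the AE page from consent to day 30, non-serious events from operating-room entry to an undated follow-up. Rates computed from that page would mix two observation periods. The Clopper-Pearson limits are the only statistical safety summary in section 9, so a reader needs to know which period and which patients they cover.

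**Working it through.** The plan states no AE rate, expected count or target precision, so there is no figure to reproduce. The check sets the windows side by side.

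| | Non-serious AE | SAE |
|---|---|---|
| Opens | Operating-room entry (6.2) | Consent (7.2.1) |
| Closes | Post-operative follow-up, undated (6.2) | Day 30 after last study drug or procedure (7.2.1) |
| Recorded on | AE page (7.1.3) | AE page and SAE form (11.1) |

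**Opening.** The order of events is consent, skin-prick and patch tests, operating-room entry. Section 1.2 puts the prick test at least 1 week before surgery, while section 6.1 puts the baseline procedures within 1 week of the observation. Those two statements need reconciling, but on either one the tests precede operating-room entry. The interval from consent to operating-room entry is therefore covered for serious events and not for non-serious ones.

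**Closing.** Assume that the follow-up in section 6.2 is the 2-3 week visit in section 6.3 (day 14 to 21), and that the last study drug or procedure is on the day of surgery (day 0). The SAE window then outlasts the AE window by 30 − 21 = 9 days to 30 − 14 = 16 days. If the follow-up means something else, the AE window has no dated end.

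**Does another section fill the gap?** Section 7.1.3 does not, because its rule applies within a period it leaves undefined. Section 11.1 does so for serious events only. What is left uncovered is non-serious events before operating-room entry and, on the assumption above, non-serious events from the visit to day 30.

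**What one unrecorded event does to the limit.** With x patients having an event out of n, the upper one-sided 95% Clopper-Pearson limit is the 0.95 quantile of a Beta(x + 1, n − x) distribution. For x = 0 this is 1 − 0.05^(1/n); at n = 30, 1 − 0.05^(1/30) = 0.095.

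| Patients with an event (assumed) | n = 10 | n = 30 |
|---|---|---|
| 0 | 25.9% | 9.5% |
| 1 | 39.4% | 14.9% |
| 2 | 50.7% | 19.5% |

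At n = 30, if the only event is one that goes unrecorded, the reported limit is 9.5% instead of 14.9%, a difference of 5.4 points. The sample sizes are the protocol's; the counts are assumed.

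**The case against.** A longer collection period for serious than for non-serious events is a legitimate choice, and sections 6.2 and 11.1 can be read together: AEs in the perioperative period, plus all SAEs. That stands. A reader might infer that skin-test reactions and late events of every kind drop out of the AE rates, or that section 11.1 contradicts section 6.2. The documents support neither, since serious events from consent to day 30 reach the AE page.

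It can also be said that the tests are not undocumented. Section 7.1.3 has abnormalities documented at baseline and AEs assessed at each evaluation. Section 6.1 has the prick test read at 30 minutes, and its outcome is an eligibility item. This stands in part: the test result will be on file, but an untoward reaction still has no stated route to the AE page. A wheal at the test or histamine-control site is a read-out, and counting expected wheals as AEs would distort the rates.

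The late gap has little bearing on dye safety. By the protocol's own account, mild fluorescein reactions typically appear 30 to 60 seconds after injection and the dye is eliminated within 24 to 36 hours (section 1.2.2). Mild ICG reactions come shortly after injection (section 1.4.2), and its plasma half-life is about 3 to 4 minutes (section 1.4). Non-serious events in weeks three and four would mostly reflect the surgery and HIPEC. This stands.

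Finally, patients with a positive prick test become ineligible and may not belong among the 30. This also stands: whether their reactions count depends on a denominator the plan does not state. The DSMB also reviews safety data annually under section 8, so the confidence limits are not the only safety oversight.

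**Conclusion.** The point holds for non-serious events, and mainly at the opening of the window. The only stated AE period begins after the study's own fluorescein and ICG skin tests, so a non-serious reaction to them has no stated place in the AE data. At the other end the close is undated. The gap of 9 to 16 days rests on equating the follow-up in section 6.2 with the 2-3 week visit, which is reasonable but not stated. The result is an AE page on which serious and non-serious events cover different periods.

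The effect on the AE rates cannot be sized from the documents. A reader might take the move from 14.9% to 9.5% at 30 patients as the bias to expect, but it only illustrates how sensitive the limit is to one event under assumed counts. Reactions in patients who then become ineligible might not enter that denominator at all. This is a minor correction to the safety data collection and does not affect the feasibility endpoint.

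**What to change.** In section 6.2, start AE recording at consent, or at the first study procedure (the skin test). Give the closing day and reconcile it with section 7.2.1. State in section 7.1.3 that this is the collection period meant there.

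Report untoward reactions to the skin-prick and patch tests, including in patients who then become ineligible, separately from intraoperative dye reactions. Exclude the expected test and histamine-control wheals. In section 9, state the window and denominator for each rate; all patients tested and all patients given intravenous dye would be natural choices for the two.

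The cost is a few sentences and slightly more AE entry, since the patient is already with the study team when the tests are done. Extending non-serious capture to day 30 would cost more, because no day-30 visit is scheduled and a contact near that day would be needed. If the sponsor prefers an earlier close for non-serious events, stating that day and presenting the rates for that period, with later serious events listed apart, would also remove the inconsistency.

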### 6.3 POST-TREATMENT FOLLOW-UP EVALUATIONS

- Standard follow-up and safety evaluations from surgery includes a post-op visit at 2-3 weeks and scheduled follow-up based upon final staging of the patient's cancer. Follow-up will be based upon current NCCN guidelines.

#### Study Calendar

	Pre-operative Visit	Surgery	Post-operative Visit
History and Physical	X		
Informed consent	X		
Fluorescein skin prick test	X		
Tests as medically indicated	X		
CRS-HIPEC with intra-op IVM		X	
Post-surgical monitoring in recovery and inpatient stay		X	
Review of pathology			X
Routine cancer surveillance			X

- At the completion of the surgery, if gross tumor is entirely debulked or ablated, then patients are considered disease free. Treatment response will be based upon the presence of a recurrence of tumor at either the primary site, locoregional recurrence (peritoneum) or metastatic sites.
- The time to recurrence will determine the standard length of clinical follow up. However, for this study, a 10-year limit will be placed on clinical data collection during the standard clinical follow up. After a patient is enrolled, the duration of data collection will end at 10 years from the time of microscopic observation (surgery). These data (time of recurrence

and/or survival) will be correlated with findings from the one-time, initial IVM observation for the defined 10-year period of data collection.

- The surveillance data (no evidence of disease, disease recurrence, death) will be stored in a secured database and matched to the microscopic observation data. These data will serve as the basis for statistical comparisons of microscopic findings and clinical outcomes to be performed by our study statistician as described in section 9.

## 6.4 PATHOLOGY

Standard pathologic evaluation (no deviation from current standard practice of pathology department) will be performed.

## 7 SAFETY EVALUATION

### 7.1 ADVERSE EVENTS

#### 7.1.1 DEFINITION

An adverse event or adverse experience (AE) is any untoward medical occurrence associated with the use of a drug in humans, whether or not considered drug related. Therefore, an AE can be **ANY** unfavorable and unintended sign (including an abnormal laboratory finding), symptom, or disease temporally associated with the use of a medicinal (investigational) product, whether or not considered related to the medicinal (investigational) product (attribution of ‘unrelated’, ‘unlikely’, ‘possible’, ‘probable’, or ‘definite’).

An AE is considered “unexpected” if it is not listed in the investigator brochure or is not listed at the specificity or severity that has been observed; or if an investigator brochure is not required or available, is not consistent with the risk information described in the general investigational plan in other study-related documents. “Unexpected” also refers to adverse events that are mentioned in the investigator brochure (or other study-related documents) as occurring with a class of drugs or as anticipated from the pharmacological properties of the drug, but are not specifically mentioned as occurring with the particular study drug.

Adverse events will be recorded in this study for the purpose of safety monitoring and adverse events are anticipated to be absent or unlikely.

#### 7.1.2 GRADING AND RELATIONSHIP TO DRUG

The descriptions and grading scales found in the CTEP Version 4 of the NCI Common Terminology Criteria for Adverse Events (CTCAE) will be utilized for AE reporting. CTEP Version 4 of the CTCAE is identified and located at: [http://ctep.cancer.gov/protocolDevelopment/electronic\\_applications/ctc.htm](http://ctep.cancer.gov/protocolDevelopment/electronic_applications/ctc.htm). AEs not covered by

specific criteria should be reported with common medical terminology and graded according to definitions provided in the CTCAE Version 4.

AEs NOT listed in the NCI-CTCAE, the severity of AEs will be graded as follows:

- **Grade 1 – Mild:** Event barely noticeable to subject; no limitation in activity, no minimal medical intervention/therapy required.
- **Grade 2 – Moderate:** Event of a sufficient severity to make participant uncomfortable. ADL limited; no or minimal medical intervention/therapy required.
- **Grade 3 – Severe:** Event causes significant discomfort/limitation in activity. May be such severity that the subject cannot continue on study. Severity may cause cessation of treatment. Treatment for symptoms may be given and/or subject hospitalized.
- **Grade 4 - Life Threatening:** Event places the participant at immediate risk of death from the reaction as it occurred. Significant medical intervention/therapy required; hospitalization or hospice care probably.
- **Grade 5 - Death.**

The relationship of event to study drug will be documented by the Investigator as follows:

- **Unrelated:** The event is clearly related to other factors such as the subject's clinical state, other therapeutic interventions or concomitant drugs administered to the subject.
- **Unlikely:** The event is doubtfully related to investigational agent(s). The event was most likely related to other factors such as the subject's clinical state, other therapeutic interventions, or concomitant drugs.
- **Possible:** The event follows a reasonable temporal sequence from the time of drug administration, but could have been produced by other factors such as the subject's clinical state, other therapeutic interventions or concomitant drugs.
- **Probable:** The event follows a reasonable temporal sequence from the time of drug administration, and follows a known response pattern to the study drug. The event cannot be reasonably explained by other factors such as the subject's clinical state, therapeutic interventions or concomitant drugs.
- **Definite:** The event follows a reasonable temporal sequence from the time of drug administration, follows a known response pattern to the study drug, cannot be reasonably explained by other factors such as the subject's condition, therapeutic interventions or concomitant drugs; AND occurs immediately following study drug administration, improves upon stopping the drug, or reappears on re-exposure.

A suspected adverse reaction is any AE for which there is a reasonable possibility that the drug caused the adverse event. Reasonable possibility means there is evidence to suggest a causal relationship between the drug and the adverse event, such as:

- A single occurrence of an event that is uncommon and known to be strongly associated with drug exposure (e.g., angioedema, hepatic injury, Stevens-Johnson Syndrome).
- One or more occurrences of an event that is not commonly associated with drug exposure, but is otherwise uncommon in the population exposed to the drug.
- An aggregate analysis of specific events observed in a clinical research study that indicates those events occur more frequently in the drug treatment group than in a concurrent or historical control group.

An AE for which there is a reasonable possibility that the drug caused the adverse event includes those assessed as having a Possible, Probable, or Definite causality assessment.

### 7.1.3 REPORTING ADVERSE EVENTS

**Table 1. Guidelines for Routine Adverse Event Reporting for Pilot Studies (Regardless of Expectedness)**

Attribution	Grade 1	Grade 2	Grade 3	Grade 4	Grade 5
Unrelated	X	X	X	X	X
Unlikely	X	X	X	X	X
Possible	X	X	X	X	X
Probable	X	X	X	X	X
Definite	X	X	X	X	X

All subjects are evaluated at baseline and any abnormalities are documented.

- Worsening abnormalities and/or worsening of a pre-existing condition (e.g., diabetes, migraine that has increased in severity, frequency or duration of the condition, or an association with significantly worse outcome) can become an AE or serious adverse event and must be documented and followed.
- A persistent AE is one that extends continuously, without resolution between treatment cycles/courses. Reporting of persistent AEs is as follows:
  - a) Routine reporting: The AE must be reported only once unless the grade becomes more severe in a subsequent cycle/course. If the grade becomes more severe the AE must be reported again with the new grade.
  - b) Expedited Reporting: the AE must be reported only once unless the grade becomes more severe in the same or a subsequent cycle/course.
- A recurrent AE is one that occurs and resolves during a cycle/course of therapy and then reoccurs in a later cycle/course. Reporting of recurrent AEs is as follows:
  - a) Routine Reporting: An AE that resolves and then recurs during a subsequent cycle/course must be reported by the routine procedures.

- b) Expedited Reporting: An AE that resolves and then recurs during a subsequent cycle/course does not require reporting unless the grade increases and hospitalization is associated with the recurring AE.
- At each evaluation, the Investigator will determine whether any AEs have occurred by evaluating the subject's signs, symptoms, and current laboratory and/or other test results.
- All AEs (expected or unexpected), including worsening of a pre-existing conditions (increased severity, frequency or duration of the condition and/or associated with significantly worse outcomes) which occur during the specified collection period, whether observed by the Investigator or by the subject, and whether or not thought to be related to study drug, will be documented in detail and followed until resolution, stabilization, death, or the start of new treatment.
- Whenever possible record a diagnosis for signs and symptoms of a common syndrome (i.e., cough, sneezing, runny nose would be reported as an upper respiratory infection).

All AEs for Pilot studies must be entered on the Adverse Event eCRF page, using the CRS EXPeRT database.

